2. SUMMARY OF KEY PROTOCOL INFORMATION

2.1. Changes to the Protocol Defined Statistical Analysis Plan

Any changes from the originally planned statistical analysis specified in the protocol are outlined in [Table 1](#).

Table 1 Changes to Protocol Defined Analysis Plan

Protocol	Reporting & Analysis Plan	
Statistical Analysis Plan	Statistical Analysis Plan	Rationale for Changes

 The protocol specified that for the primary efficacy analysis 'Historical placebo information with 50% weight will be incorporated into the mixed effect model by Bayesian modelling using SAS PROC MCMC procedure'. Also, 'The above repeated mixed-effects model analysis will be repeated without placebo information from DEFEND-1, and with 100% placebo information from the DEFEND-1 study as sensitivity analyses' 	
 The primary efficacy analysis using 50% weight for historical information has been replaced by a Bayesian analysis which incorporates historical placebo data from the DEFEND-1 study using a robust mixture prior. The weighting for the robust mixture prior will be $w=0.5$. The sensitivity analyses without placebo data from DEFEND-1 and using 100% placebo data from DEFEND-1 will be performed using $w=0$ and $w=1$ respectively. 	
 This methodology allows the weighting of historical DEFEND-1 placebo data to depend on the similarity to the albiglutide GLP110933 study data. It has been recommended as an improved approach by experts on Bayesian analysis within GSK.

 The protocol describes the primary Bayesian analysis as a mixed-effects model. 	
 The RAP has removed the terminology 'mixed-effects' from the description of the Bayesian analysis. 	
 The Bayesian approach is to treat all parameters as random. This change was recommended as an improved description of the Bayesian analysis.

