2.4. Statistical Hypotheses

For this Phase II, randomised, multicentre, double-blind, placebo controlled study, the primary objective is to evaluate the efficacy of albiglutide versus placebo on endogenous insulin secretion. The primary efficacy analysis endpoint will be change from baseline stimulated 2 hour MMTT C-peptide AUC at Week 52 following one year of treatment.

The primary endpoint analysis, incorporating historical placebo data from the DEFEND-1 study, will be performed using a Bayesian analysis and will therefore not utilise hypothesis testing.

However, in a non-Bayesian sensitivity analysis of the primary endpoint (excluding historical placebo data from the DEFEND-1 study) the treatment effect will be evaluated using the least squares means contrast relative to placebo. This contrast will be evaluated inferentially with a 2-sided t-test at the 0.05 criterion significance level.

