weakly informative prior is Normal with large variance,

w is how robust the prior is considered to be e.g. w=0 is pure weakly informative prior; w=1 is the historical prior.

The weighting of the DEFEND-1 placebo data depends on its similarity to the GLP110933 study placebo data. The mixture prior down-weights the historical data when the historical data does not agree with the GLP110933 study placebo data. The mixture prior up-weights the historical data when the historical data agrees with the GLP110933 study placebo data. The choice of w determines how quickly historical information is discounted as prior-data conflict increases. The primary analysis will use a w value of 0.5; this corresponds to the choice of 50% weighting for the primary analysis as planned in the protocol.

The model will use a general (unstructured) covariance matrix as specification for the covariance among observations from the same subject. The model will provide an unbiased treatment difference estimate for the Week 52 time point, with better precision

achieved by accounting for intra subject variability than an analysis of covariance approach. In the event of missing observations at Week 52, the planned analysis and test are valid under a “missing at random (MAR)” assumption where missing data may depend on prior observations.

This Bayesian analysis will derive the posterior distribution for the C-peptide treatment difference (Albiglutide – placebo), which will be plotted and an estimate of the treatment difference (median) and 95% (highest posterior density (HPD)) credible interval will be produced, together with the construction of the following probability statements:

- probability that the treatment difference ≥ 0.2 nmol/L (clinically relevant “good effect”)
- probability that the treatment difference is ≥ 0.1 nmol/L (clinically relevant “some effect”)
- probability that the treatment difference ≥ 0 nmol/L (“no effect”).

Sensitivity Analysis (MMRM with weighting of 0% and 100% DEFEND-1 Placebo Data) – All On-Study Data

Sensitivity analyses will be performed for the primary Bayesian analysis using PROC MCMC, repeating the analysis described above but using the following values for w:

- w=0; corresponding to without historical placebo data.
- w=1; corresponding to 100% historical placebo data.

Non-Bayesian Sensitivity Analysis (MMRM) – All On-Study Data

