As a further sensitivity analysis, a non-Bayesian repeated measures mixed effect model using PROC MIXED will be fitted, using all valid efficacy assessments during the study period. This model will not include any historical placebo data from the DEFEND-1 study. This analysis will be performed using the MMRM approach, as described for the secondary endpoints in Section 8.1.2 (change from baseline in stimulated (from MMTT) 2 hour plasma C-Peptide AUC at Week 16, 28 and 64). For this analysis only:

A test of the treatment group difference at Week 52 will be provided by the comparison of the appropriate treatment group-by-visit least square means (LS means).

The difference will be considered significant if the two sided p-value for the comparison between treatments in change from baseline 2 hour MMTT C-peptide AUC is less than or equal to 0.05. The corresponding 95% confidence intervals will also be presented.

Additional sensitivity analyses are described in Section 7.1.2.

The details regarding MMTT assessments are provided in Section 11.11.

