
Primary Statistical Analyses

 ○ Note: the initial parameter values will be used for all parameters in the model (as specified above) with the exception of the covariance matrix of the likelihood function which will use SAS default initial parameters for all chains. ● Initially each chain will run with a simulation size of 50000 (NMC=50000) and all three chains will be included to provide the posterior distribution summaries, treatment differences and construct probability statements (i.e. using a total of 150000 posterior observations). ● SAS provided macros, including %POSTSUM, %TADPLOT and %POSTINT, will be used to provide summaries of the posterior distribution (including 95% HPD credible intervals). ● Thinning will not be used (THIN=1) ● Initially the SAS default of 1000 iterations will be used for the number of burn-in's (NBI=1000) ● For tuning, the following values will be specified: MINTUNE=5, MAXTUNE=500 and NTU=2000. ● Convergence will be assessed using the Gelman & Rubin diagnostic, examining trace plots for model parameters, assessing the Effective Sample Size (ESS) and Geweke diagnostics. The ratio of the Monte Carlo Standard Error (MCSE) to the SD of the posterior will also be assessed. If the model does not converge then the number of burn-in's (NBI), the number of simulations (NMC) and the tuning values may be adjusted, as appropriate, in order to improve model convergence. The numbers by which MCMC iterations and burn-in iterations need to be increased may be significant. Additional adjustments to the model may be necessary if convergence is not improved. ● Historical placebo data from 53 subjects from the DEFEND-1 study will be incorporated as the prior distribution for the Week 52 visit using the robust mixture prior as follows: 
 ○ From DEFEND-1, N = 53 and the mean change from baseline was -0.269, SD = 0.314 and SE = 0.043. ○ The historical prior will be specified as Normal (-0.269, SE=0.043) ○ The weakly informative prior will be specified as Normal (0, SE=1000); ○ $I_{prior} = \log [w * pdf (historical prior) + (1-w) * pdf (weakly informative prior)]$ ○ Prior (week 52 placebo) \sim General (I_{prior}) ● Priors for other parameters (including placebo at other visits) will be specified as Normal (0, var=1E6)
Model Checking & Diagnostics

 ● Convergence of the Bayesian model will be assessed as described above.
Model Results Presentation

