11.6. Appendix 6: Premature Withdrawals & Handling of Missing Data

11.6.1. Premature Withdrawals

Element	Reporting Detail
General	
 Subject study completion (i.e. as specified in the protocol) was defined as completion of all periods of the study up to and including the follow-up period. The protocol specified that 'if the withdrawal rate from the study is larger than expected, consideration will be given to replacing subjects who withdraw from the study.'. However due to poor enrolment a decision was made that withdrawn subjects would not be replaced in the study. All available data from subjects who were withdrawn from the study will be listed and all available planned data will be included in summary tables and figures, unless otherwise specified.

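### With a vague component of SE=1000, the w=0.5 mixture prior borrows almost all of DEFEND-1 unless the two placebo groups differ by more than about 0.2 nmol/L

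*SAP*

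**What the plan says.** Protocol 8.2.2 plans for DEFEND-1 to contribute 50% of its placebo information, and protocol 8.3.5.3.1 carries that weight into the primary model. SAP 2.1 replaces this with a robust mixture prior, on the ground that "This methodology allows the weighting of historical DEFEND-1 placebo data to depend on the similarity to the albiglutide GLP110933 study data".

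SAP 7.1.2 gives the historical component as Normal(-0.269, SE 0.043), from 53 subjects with SD 0.314. For the other component it says "The weakly informative prior will be specified as Normal (0, SE=1000". The 1000 is not a slip for a variance, because the priors on the other parameters use a variance of 1E6, which is the same scale.

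SAP 7.1.1.1 makes three claims about how the prior behaves. One links the new weight to the old: "The primary analysis will use a w value of 0.5; this corresponds to the choice of 50% weighting for the primary analysis". Another is that borrowing adapts to what is observed, since "The mixture prior down-weights the historical data when the historical data does not agree with the GLP110933 study placebo data". Thirdly, it says that the size of w sets the speed of this discounting.

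The planned variations are w=0, w=1 and a non-Bayesian MMRM, of which the SAP says "This model will not include any historical placebo data from the DEFEND-1 study". Nowhere is the scale of the vague component justified or varied, and no operating characteristics are given.

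**The concern.** In a mixture prior, the posterior weight on history depends on w and on how thinly the vague component is spread. A component with SD 1000 nmol/L has almost no density near any plausible placebo mean, so it loses to the historical component even when the two placebo groups clearly disagree. The dependence on similarity, which was the reason for leaving the protocol's method, would then be missing over the range of drift that matters.

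The primary estimate, its 95% credible interval and the three probability statements would then rest mainly on another trial's placebo group. Agreement between the primary and w=1 analyses would look like robustness but be nearly built in. Some disagreement is plausible from the documents. The DEFEND-1 values include LOCF, while this trial uses repeated measures. DEFEND-1 also required two post-meal samples for an AUC, and this trial requires one (SAP 4 and 11.5.4). Neither point proves drift.

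**Working it through.** **The plan's own figures.** Take SD 0.31, 45 albiglutide subjects, placebo n = 15 + weight × 53, and a two-sided 0.05 normal approximation. Power at a difference of 0.20 is then 58.1, 78.9, 85.0, 88.7 and 91.9% for weights 0, 30, 50, 70 and 100%. Protocol Table 5 gives 58, 78, 85, 89 and 92%. The minimal detectable differences, 1.96 × SE, are 0.181, 0.142, 0.131, 0.124 and 0.117, which match Table 6. The prior SE is 0.314/√53 = 0.043. The plan's figures therefore reproduce, and its 50% means 15 + 26.5 = 41.5 placebo subjects.

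**Posterior weight on DEFEND-1.** Assume 15 evaluable placebo subjects (protocol 8.2.1) and residual SD 0.314 (SAP 7.1.2), treated as known.

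- SE of the current placebo mean: 0.314/√15 = 0.0811.
- SD of its predictive distribution under the historical component: √(0.043² + 0.0811²) = 0.0918. Under the vague component it is 1000.
- Density ratio, historical to vague, at an observed difference d between the placebo means: (1000/0.0918) × exp(−d²/(2 × 0.0918²)) = 10,897 × exp(−d²/(2 × 0.0918²)).
- Posterior weight: W = w × ratio / (w × ratio + 1 − w).

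At d = 0.20 the ratio is 10,897 × exp(−2.375) ≈ 1,014, so with w = 0.5, W = 1,014/1,015 = 0.999. The 50% point is 0.0918 × √(2 ln 10,897) = 0.396 nmol/L.

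| Observed difference (nmol/L) | W as written, SD 0.314 | W as written, SD 0.20 | W with vague part Normal(-0.269, SD 0.314) |
|---|---|---|---|
| 0 | 0.9999 | 0.9999 | 0.78 |
| 0.10 | 0.9998 | 0.9998 | 0.67 |
| 0.20 | 0.999 | 0.994 | 0.28 |
| 0.30 | 0.98 | 0.41 | 0.03 |

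A difference of 0.20 is the SAP's own threshold for a good effect, and it is 0.20/0.0918 ≈ 2.2 standard errors.

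**Effect of w.** At d = 0.20, w = 0.1, 0.5 and 0.9 give W = 0.991, 0.999 and 0.9999. The 50% point moves only from 0.346 to 0.396 to 0.440. Changing the vague SD to 0.314, 1 or 10, with w = 0.5, moves it to 0.15, 0.20 or 0.28.

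**Amount borrowed when W is near 1.** Effective placebo n = 15 + 0.314²/0.043² = 68.3. DEFEND-1's share of the placebo estimate is (1/0.043²)/(1/0.043² + 15/0.314²) = 78%. The range is 59 to 84% over SD 0.20 to 0.314 and n 10 to 15.

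**Consequence, by simulation.** There were 400,000 trials per scenario, 15 and 45 subjects, SD 0.314 and no drug effect. The SAP sets no success threshold, so P(difference ≥ 0) ≥ 0.975 is used as an illustration.

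| True placebo shift | Bias as written | Signal: as written | Signal: w=1 | Signal: fixed 50% | Signal: Normal(-0.269, SD 0.314) |
|---|---|---|---|---|---|
| +0.10 | 0.08 | 21% | 21% | 11% | 7% |
| +0.20 | 0.15 | 71% | 78% | 47% | 9% |

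Downward shifts mirror these rates as false signals of harm. At SD 0.20 the biases are 0.06 and 0.11, with rates of 22% and 65%. At 10 and 30 subjects the rates are 19% and 66%. With a true effect of 0.20 and a shift of −0.20, benefit is signalled in about 7% of trials, against 57% with no borrowing.

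**The case against.** The strongest reply is that most of this bias comes with borrowing itself, which the protocol chose. Fixed 50% borrowing gives biases of 0.064 and 0.128 at shifts of 0.10 and 0.20, against 0.078 and 0.151 here, and DEFEND-1 would still supply 26.5/41.5 = 64% of the placebo estimate. At a shift of 0.269 the mixture's false-signal rate (about 70%) is below that of fixed 50% borrowing (about 76%). This stands as context: the 71% is not all due to SE=1000. It does not rescue the claims in SAP 7.1.1.1, because the mixture was adopted to do better than a fixed weight, and up to about 0.2 nmol/L it does worse.

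It is also true that large conflict is discounted (W is about 0.06 at 0.45 nmol/L), that w has some effect, and that the documents show no evidence of a 0.20 shift. With no drift, the two-sided false-signal rate is about 1.8%.

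Finally, the primary analysis "will be performed using a Bayesian analysis and will therefore not utilise hypothesis testing", so no formal decision hangs on it. The w=0 analysis, the MMRM and the side-by-side placebo summaries let a reader see the unborrowed result and any conflict. These limit the harm, but they leave the primary estimate, interval and probabilities unchanged.

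**Conclusion.** The concern holds and should be corrected before unblinding. For placebo differences up to about 0.2 nmol/L, the prior as written is close to full borrowing, at about 68 effective placebo subjects instead of 41.5. Setting w=0.5 does not correspond to 50% weighting. Down-weighting is negligible in that range, and the unexplained 1000, not w, controls the borrowing.

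The calculation treats the SD as known and ignores baseline and age adjustment and the repeated measures. The documents fix neither the adjusted SD nor the final numbers, and SAP 11.6.1 records that "due to poor enrolment a decision was made that withdrawn subjects would not be replaced in the study". Over SD 0.20 to 0.314 and n 10 to 15, the posterior weight at 0.20 nmol/L stays at 0.994 or above, so the conclusion does not depend on those assumptions. The false-signal rates do depend on the illustrative cut-off; the bias does not.

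**What to change.** Before unblinding:

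1. In SAP 7.1.2, replace SE=1000 in the Week 52 placebo mixture with a component on the endpoint's scale, and justify the choice. A unit-information component, Normal(-0.269, SD 0.314) with w=0.5, is one example. Its centre is also a choice: a version at zero with SD 0.31 gives similar weights (0.83, 0.69 and 0.24 at differences of 0, 0.10 and 0.20).
2. Pre-specify a table of posterior weight against placebo difference for the chosen scale and its alternatives.
3. Report the posterior mixture weight and effective sample size with the primary result.
4. Delete the sentence equating w=0.5 with 50% weighting.
5. Keep w=0, w=1 and the non-Bayesian MMRM. Any between-trial variance can only be a sensitivity analysis over an assumed range, because one historical study cannot estimate it.

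This needs SAP wording and one line of PROC MCMC code, with no patients or new data. The price is precision. If the trials agree, the 95% half-width goes from 0.118 to about 0.135 nmol/L under the unit-information example, close to the 0.132 of fixed 50% borrowing and below the 0.183 of none. At a true effect of 0.20 with no drift, the illustrative benefit-signal rate falls from 95% to 78%, against 89% for fixed 50% borrowing and 57% for none.

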8. SECONDARY STATISTICAL ANALYSES

8.1. Efficacy Analyses

8.1.1. Overview of Planned Efficacy Analyses

The secondary efficacy analyses will be based on the “Intent-To-Treat” population, unless otherwise specified.

Table 5 provides an overview of the planned efficacy analyses, with further details of data displays being presented in [Appendix 13: List of Data Displays](#).

Table 5 Overview of Planned Efficacy Analyses

Secondary Efficacy Endpoints	Absolute						Change from Baseline					
	Stats Analysis			Summary		Individual	Stats Analysis			Summary		Individual
	T	F	L	T	F	F	T	F	L	T	F	F
Mixed Meal Tolerance Test (Baseline, Week 16, 28, 52, 64)												
Stimulated (from MMTT) 2 hour plasma C-peptide AUC ^[3]				Y ^[1]	Y		Y	Y		Y ^[1]	Y	
Plasma Glucagon AUC (from MMTT)				Y ^[1]	Y		Y	Y ^[4]		Y ^[1]		Y
Maximum plasma C-peptide during 2hr MMTT				Y ^[1]	Y		Y	Y ^[4]		Y ^[1]		Y
Percent of Responders (Baseline, Week 4, 8, 16, 28, 40, 52 and 64)												
HbA1c ≤7.0 and insulin dose<0.5 units/kg/day	Y ^[4]			Y	Y		Y					
IDAA1C ≤9	Y ^[4]			Y	Y		Y					
Glucose Control (Baseline, Week 4, 8, 16, 28, 40, 52 and 64)												
HbA1c				Y ^[1]	Y		Y	Y ^[4]		Y ^[1]		Y
Mean daily insulin dose				Y ^[1]	Y		Y	Y ^[4]		Y ^[1]		Y
Subject-Reported Hypoglycaemic Events												
Number of hypoglycaemias with confirmed plasma glucose monitoring ≤3.9 mmol/L and/or requiring third party intervention occurring >Week 24 and ≤Week 52				Y ^[2]			Y					

Secondary Efficacy Endpoints	Absolute							Change from Baseline						
	Stats Analysis			Summary		Individual		Stats Analysis			Summary		Individual	
	T	F	L	T	F	F	L	T	F	L	T	F	F	L
7-Point Glucose Profile														
Glucose levels at each of the 7 specified time-points of the 7-point glucose profile at Baseline, Week 28 and Week 52				Y										
Number of hypoglycaemic excursions (≤ 3.9 mmol/L) from 7-point glucose profile				Y										
Proportion of subjects with hypoglycaemic excursions from 7-point glucose profile				Y										
Greatest magnitude of hypoglycaemic excursion from 7-point glucose profile				Y										
Number of hyperglycaemic excursions (>10 mmol/L) from 7-point glucose profile				Y										
Proportion of subjects with hyperglycaemic excursions from 7-point glucose profile				Y										
Greatest magnitude of hyperglycaemic excursion from 7-point glucose profile				Y										
Listing of data from 7-point glucose profile								Y						
72-hr CGM (Baseline, Week 28, 52)														
Proportion of time spent with plasma glucose ≤ 3.9 mmol/L; between >3.9 and 10.0 mmol/L; and >10.0 mmol/L				Y ^[1]	Y		Y	Y ^[4]			Y ^[1]	Y		Y
Weight (Baseline, Week 2, 4, 6, 8, 16, 28, 40, 52 and 64)														
Body weight (kg)				Y ^[1]	Y		Y	Y ^[4]			Y ^[1]			Y

NOTES :

- T = Table, F = Figure, L = Listing, Y = Yes display generated.
- Stats Analysis = Represents TFL related to any formal statistical analyses (i.e. modelling) conducted.
- Summary = Represents TFL related to any summaries (i.e. descriptive statistics) of the observed raw data.
- Individual = Represents FL related to any displays of individual subject observed raw data.
- [1] Absolute and change from baseline summaries combined into a single display
- [2] Summary table will also be produced for the Baseline to Week 24 time-period.
- [3] MMTT C-peptide AUC: week 52 time-point is the primary efficacy endpoint, refer to Section 7 for details of statistical analysis.
- [4] Statistical analysis performed at Week 28 and Week 52 only

8.1.1.1. Supplementary Information for Subject-Reported Hypoglycaemic Events

Subject-reported hypoglycaemic events (see Section 11.5.3 and Section 11.5.4) will be used for this endpoint. This endpoint will determine any differences in significant hypoglycaemia (i.e., events with plasma glucose ≤ 3.9 mmol/L and/or requiring third party intervention); that is severe, documented symptomatic and asymptomatic hypoglycaemic events as defined by ADA category.

Incidence of severe hypoglycaemia, documented symptomatic hypoglycaemia, and asymptomatic hypoglycaemia will be tabulated by treatment group. Incidence is defined as the numbers of subject-reported hypoglycaemic events per subject, and total percentages of subjects affected. The summary table will present the average number of events per subject (i.e. the number of subject reported hypoglycaemic events divided by the number of subjects), incidence (percentages of subjects affected) and the number of events occurring by treatment group. The summary will be produced for the time period from Baseline to Week 24, and from > Week 24 to \leq Week 52.

Further exploratory analysis may be done, depending on the amount of missing data.

8.1.1.2. Supplemental Information for Plasma Glucagon (from MMTT)

There was a change to the lower limit of quantification for the plasma glucagon test at the laboratory during the course of the study. This would be an issue at the individual subject level if the lower limit at the baseline visit was different to the lower limit used for subsequent visits. Further explanation and details on how this will be handled can be found in Section 11.5.4.

8.1.2. Planned Efficacy Statistical Analyses

Secondary Statistical Analyses	
Endpoint(s)	

 Change from baseline in stimulated (from MMTT) 2 hour plasma C-Peptide AUC at Week 16, 28 and 64 Change from baseline in maximum stimulated plasma C-Peptide at Week 28 and 52 Change from baseline in plasma glucagon AUC (from MMTT) at Week 28 and 52 Change from baseline in HbA1c (%) at Week 28 and 52 Change from baseline in mean daily insulin use at Week 28 and 52 Change from baseline in body weight (kg) at Week 28 and 52 	
Model Specification	

 Endpoints will be statistically analysed using a mixed models repeated measures (MMRM) model, using PROC MIXED in SAS. All post-baseline scheduled visits will be included in the analysis (as appropriate to the endpoint) using nominal visit. [Including Week 52 for C-peptide AUC] The mixed effects model will use a general (unstructured) covariance matrix as specification for the covariance among observations from the same subject. A test of the treatment group difference at each visit will be provided by the comparison of the appropriate treatment group-by-visit least square means (LS means). Terms fitted in the MMRM model will include: 
Dependent variable: Change from Baseline
 
Fixed categorical: Treatment, Visit, Treatment-by-Visit Interaction
 
Fixed Continuous Covariates: Baseline, Age (years)
 
Repeated Effect: Visit with Subject as the blocking variable
 
Covariance Matrix: General (Unstructured) #
 
# If the model fails to converge, a less stringent correlation matrix will be specified – to be decided based upon model convergence status and Akaike information criteria (AIC)
 Inclusion of the term baseline-by-visit may be considered in the final model based on model fit and/or convergence. Model parameter estimates will be computed estimates will be computed by the restricted maximum likelihood (REML) method. The Kenward-Roger approximation will be used to estimate denominator degrees of freedom for tests. 	
Model Checking & Diagnostics	

 Refer to Appendix 9: Model Checking and Diagnostics for Statistical Analyses. 	
Model Results Presentation	

 Least squares means and corresponding standard error of means (SEs) for change from baseline will be presented for each treatment group at each time-point. The estimated treatment difference, associated 95% confidence interval and p-value will be presented at each time-point. 	

Secondary Statistical Analyses	
Summary TFLs	

 Summary statistics for absolute and change from baseline will be presented for each treatment group at all visits (including visits with no statistical analysis performed) For C-peptide AUC, plots of mean absolute (\pm SE) and mean change from baseline (\pm SE) will be presented for each treatment group over time For other endpoints, plots of mean absolute (\pm SE) will be presented for each treatment group over time Data will be listed. 	
HbA1c	

 Statistical analysis of HbA1c will be performed using HbA1c in units of %. Summary statistics for absolute and change from baseline will be presented in units of % and in units of mmol/mol Plots will be presented using units of % Data listings will contain both units of % and units of mmol/mol 	
Endpoint(s)	

 Percentage of Responders (defined as subjects with HbA1c \leq 7.0 and mean daily insulin use <0.5 units/kg/day) at Week 28 and 52 Percentage of subjects achieving partial remission status (i.e., insulin dose-adjusted haemoglobin A1c [IDAA1C] \leq 9.0) at Week 28 and 52 	
Model Specification	

 The treatment comparison will be undertaken with a non-parametric, covariance-adjusted, extended Mantel-Haenszel test using the SAS FREQ procedure. Age (categorical) will be included as a covariate. This technique is especially suited for situations in which covariance adjustment is needed to optimise statistical power, while minimizing the modeling assumptions. 	
Model Checking & Diagnostics	

 Not applicable 	
Model Results Presentation	

 The odds ratio, associated 95% confidence interval and p-value for the treatment difference will be presented at each time-point. 	
Additional Covariate Information	

 In this analysis, age will be included as a categorical covariate. Age will be dichotomised into a binary variable, based on whether a subject's age is above or below the median age (overall subjects in the ITT population). Age categories: $<$ median age (years); \geq median age (years) 	
Missing data	

 In a change from the planned analysis, the LOCF method will not be used for HbA1c and insulin usage. All available data will be used for the analysis. A post-hoc sensitivity analysis imputing missing data may be performed if needed, but is not currently planned to be performed. If a subject has missing HbA1c/insulin use data and the reason why the value is missing is not related to efficacy or safety (e.g., procedural) and could be assumed that the value is missing at random, then the value would be left as missing for calculations; if the reason why the value is missing is lack of efficacy or due to safety, then this missing value would be imputed as 'not meeting target' and included in the denominator in the calculations of the proportion of responders. See Section 11.6.2.2 for further details. 	

Secondary Statistical Analyses
Summary TFLs

Responders/Partial Remission:
 
 • The proportion of responders (number and percentage) will be presented for each treatment group at all visits (including visits with no statistical analysis performed). • The proportion of responders over time will be presented graphically for each treatment group. • Data will be listed.
Endpoint(s)

 • Number of events of hypoglycaemia with confirmed self plasma glucose monitoring ≤ 3.9 mmol/L and/or requiring third party intervention (i.e. severe, documented symptomatic and asymptomatic hypoglycaemic events) occurring $>$Week 24 and \leqWeek 52. • Number and magnitude of hypoglycaemic (≤ 3.9 mmol/L) excursions from the 7-point glucose profile at Baseline, Week 28 and Week 52 • Number and magnitude of hyperglycaemic (>10.0 mmol/L) excursions from the 7-point glucose profile at Baseline, Week 28 and Week 52
Model Specification

 • Formal comparative statistical analysis will not be performed for these endpoints.
Model Checking & Diagnostics

 • Not applicable.
Model Results Presentation

 • Not applicable.
Summary TFLs

Subject-Reported Hypoglycaemic Events:
 
 • For the time periods (Baseline to Week 24; $>$Week 24 \leqWeek 52): the average number of significant events per subject (i.e. number of subject-reported events divided by the number of subjects); percentage of subjects reporting significant events; and the total number of significant events; will be presented for each treatment group. • Data will be listed.

7-point glucose profile:
 
 • The glucose level at each of the 7 specified timepoints of the 7-point glucose profile will be summarised for each treatment group using descriptive summary statistics. • The number and percentage of subjects with any hypoglycaemic excursions will be presented for each treatment group. • The number of hypoglycaemic excursions that each subject experienced will be summarised for each treatment group using descriptive summary statistics. • The greatest magnitude of hypoglycaemic excursion of each subject will be summarised for each treatment group using descriptive summary statistics • The summaries will be repeated for hyperglycaemic excursions. • Data will be listed.
Endpoint(s)

 • Proportion of time spent with plasma glucose ≤ 3.9 mmol/L; between >3.9 and 10.0 mmol/L; and >10.0 mmol/L (72h CGM) at Baseline, Week 28 and Week 52.

Secondary Statistical Analyses	
Model Specification	

 Change from baseline in time spent (h/day) with plasma glucose ≤ 3.9 mmol/L at Week 28 and Week 52; Change from baseline in time spent (h/day) with plasma glucose between >3.9 and 10.0 mmol/L at Week 28 and Week 52; Change from baseline in time spent (h/day) with plasma glucose >10.0 mmol/L at Week 28 and Week 52; Statistical analysis will be performed separately for the 3 endpoints, however care should be taken when interpreting results as due to the nature of the endpoints the data is linked. The endpoints will be statistically analysed using separate mixed models repeated measures (MMRM) models, using PROC MIXED in SAS. The analysis will be performed as described for the secondary endpoints using the MMRM methodology. 	
Model Checking & Diagnostics	

 Refer to Appendix 9: Model Checking and Diagnostics for Statistical Analyses. Due to the correlation between the 3 endpoints, a multivariate (MANOVA) approach may additionally be explored. 	
Model Results Presentation	

 Least squares means and corresponding standard error of means (SEs) for change from baseline will be presented for each treatment group at each time-point. The estimated treatment difference, associated 95% confidence interval and p-value will be presented at each time-point. 	
Summary TFLs	

 The proportion of time spent with plasma glucose ≤ 3.9 mmol/L; between >3.9 and 10.0 mmol/L; and >10.0 mmol/L will be presented for each treatment group at Baseline, Week 28 and Week 52 using descriptive statistics. Results presented in both hours/day and %. Change from baseline in the proportion of time spent with plasma glucose ≤ 3.9 mmol/L; between >3.9 and 10.0 mmol/L; and >10.0 mmol/L will be presented for each treatment group at Week 28 and Week 52 using descriptive statistics. Results presented in both hours/day and %. A pie chart will be presented for each treatment/visit showing the mean hours/day spent in each of the 3 plasma glucose categories. A bar chart will be presented for each of the 3 glucose categories showing the change from baseline in the mean hours/day spent in that plasma glucose categories for each treatment group at Week 28 and Week 52. Results presented as %. Data will be listed, including time spent in each of the 3 plasma glucose categories. 	

